| Estimated Enrollment Period | 36 months | | |
| Estimated Study Duration | 48 months | | |

| KEY | Inclusion Criteria |
|-------------|------------------------------------------------------------------------------|
| ELIGIBILITY | 1. Male or female, age \geq 18 years at the time of informed consent. |
| CRITERIA | 2. Capable and willing to sign informed consent form prior to performing any |
| | |

- protocol-related procedures.
- 3. Histologic or cytologic evidence of advanced or metastatic biliary tract cancer, including cholangiocarcinoma (intra-hepatic or extra-hepatic bile ducts), ampullary carcinoma, or gallbladder carcinoma.
- 4. Evidence of recurrent, locally advanced, unresectable, or metastatic disease.
- 5. Progressed following or intolerant to one or more lines of systemic therapy, or treatment-naïve subjects who either decline or being considered not a good candidate first-line systemic chemotherapy per the opinion of the treating physician
- 6. Per the opinion of the physician investigator, predicted life expectancy > 3 months.
- 7. Presence of at least 1 lesion that is measurable or evaluable using Response Evaluation Criteria in Solid Tumors (RECIST) v1.1.
- 8. Eastern Cooperative Oncology Group (ECOG) performance score of ≤ 2 .
- 9. Per the opinion of the physician investigator, acute toxicities relating to any prior anticancer treatment have improved to Grade 1 or baseline. Exceptions include residual alopecia or Grade 2 peripheral neuropathy.
- 10. Ability to swallow capsules.
- 11. Adequate organ function as evidenced by the laboratory parameters noted in Section 3.0 Study Eligibility.
- 12. Women of childbearing potential (WOCP) defined as not surgically sterile (hysterectomy, tubal ligation, or oophorectomy), or at least 1 year postmenopausal, must have a negative serum pregnancy test before study drug administration on cycle 1 day 1.
- 13. WOCP must use a medically acceptable method of contraception and must agree to continue used of this method for the duration of the study and for 3 weeks after last dose of study drug. Acceptable methods of contraception include abstinence, barrier method with spermicide, intrauterine device (IUD) known to have a failure rate of less than 1% per year, or steroidal contraceptive (oral, transdermal, implanted, or injected) in conjunction with a barrier method.

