3.0 SELECTION OF PARTICIPANTS/ELIGIBILITY

3.1 Inclusion Criteria:

- 1. Male or female, age \geq 18 years at the time of informed consent.
- 2. Capable and willing to sign informed consent form prior to performing any protocol-related procedures.
- 3. Histologic or cytologic evidence of advanced or metastatic biliary tract cancer including cholangiocarcinoma (intra-hepatic or extra-hepatic), ampullary carcinoma, or gallbladder carcinoma.
- 4. Evidence of recurrent, locally advanced, unresectable, or metastatic disease.
- 5. Progressed following or intolerant to one or more lines of systemic therapy, or treatment-naïve subjects who either decline or being considered not a good candidate first-line systemic chemotherapy per the opinion of the treating physician
- 6. Per the opinion of the physician investigator, predicted life expectancy of >3 months.
- 7. Presence of at least 1 lesion that is measurable or evaluable using RECIST v1.1.
- 8. ECOG performance score ≤ 2 .
- 9. Per the opinion of the physician investigator, acute toxicities relating to any prior anticancer treatment have improved to Grade 1 or baseline. Exceptions include residual alopecia or Grade 2 peripheral neuropathy.
- 10. Ability to swallow capsules.
- 11. Adequate organ function, as evidenced by all of the following:

| System | Laboratory value | | |
|-------------|---------------------------------------------------------------------------------------------------------------------------------------------------------------------------------------------------------------------------|--|--|
| Hematologic | | | |
| ANC | ≥1500/µL | | |
| Platelets | ≥75,000/µL | | |
| Hemoglobin | ≥8.0 g/dL (Patients may receive erythrocyte transfusions to achieve this hemoglobin level at the discretion of the investigator. Initial treatment may not begin earlier than the day after the erythrocyte transfusion.) | | |

| System | Laboratory value | | |
|-----------------------|---------------------------------------------------------------------------------------------------------------------------------------------------|--|--|
| Hepatic | | | |
| Serum total bilirubin | ≤2 times the ULN; Patients with Gilbert's syndrome with a total bilirubin ≤3.0 times ULN and direct bilirubin within normal limits are permitted. | | |
| AST and ALT | ≤3 times the ULN, ≤ 5 times ULN for subjects with liver metastasis | | |

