7.0 STUDY DESIGN AND PROCEDURES

This is a open label pilot study of abemaciclib administered orally to participants with recurrent, locally advanced, unresectable, or metastatic BTC. This study consists of a screening period of up to 28 days, up to eight 28-day treatment cycles, an EOT visit and follow-up visits every 3 months (\pm 7 days) 6 months after last dose of the study drug then every 6 months(\pm 7 days) thereafter until death .

The Principal Investigator will determine whether the participant meets all inclusion/exclusion criteria.

Each cycle will consist of 28 days of twice daily dosing of abemaciclib. Participants must receive a minimum of two 28 day cycles to be considered evaluable for the primary endpoint of ORR unless they withdraw earlier due to rapid disease progression. If a participant is deriving clinical benefit, he or she may receive additional cycles until one of the criteria for discontinuation is met.

Participants who are deriving clinical benefit after completing the treatment period may continue on additional cycles of therapy at the discretion of the sponsor and the medical monitor from the DSMC. Any participant that continues on abemaciclib after completing the treatment period will be monitored and assessed for tumor response per clinical routine per principal investigator.

Participants who complete treatment or who are withdrawn from treatment early will have an end of treatment visit. Participants with measurable disease who end treatment on a cycle at which a tumor response assessment is not planned should have end of treatment CT scans/MRI scans. Follow up visits will be performed every three months \pm 4 days 6 months for the subsequent anticancer therapy and survival then thereafter every 6 months (\pm 7 days) for survival only till death. It will be done by either clinic visit or phone call.

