7.7.1 Assessment of Tumors by RECIST v 1.1

Tumor assessments that are made after administration of study drug will be compared with those obtained at baseline or the smallest sum since treatment started, to determine whether CR, PR, SD or PD has occurred.

Measurable disease, measurable lesions, and non-measurable lesions are defined as follows:

- Measurable disease: presence of at least 1 measurable lesion after the histological diagnosis and staging of disease
- Measurable lesions: lesions that can be accurately measured in at least 1 dimension as 10 mm or greater and lymph nodes ≥ 15 mm in shortest axis by CT scan measurements (or MRI, as appropriate); prior sites of loco-regional therapy (e.g., fibrosis from radiation) should not be considered measurable lesions
- Non-measurable lesions: all other lesions including skin lesions, small lesions (less than 10 mm), lymph nodes < 15 mm and > 10 mm in shortest axis, ascites, pleural/pericardial effusions, etc.

Documentation of lesions should include date, site, dimensions, description, and diagnostic method. The same method of assessment and technique should be used at baseline and during follow-up to characterize each identified and reported lesion.

Baseline documentation of target and non-target lesions is as follows: all measurable lesions up to a maximum of 5 lesions total and a maximum of 2 lesions per organ representative of all involved organs should be identified as target lesions.

Response Evaluation Criteria in Solid Tumors (RECIST, Version 1.1)

| Measurable tumor burden | Maximum 5 target lesions in total (up to 2 per organ) can be identified at baseline and measured through the course of therapy | |
|----------------------------------|-------------------------------------------------------------------------------------------------------------------------------------------------------------------------------------------------------------------------------------------------------------|--|
| Minimum | ≥10 mm in LD and 2 times the slice thickness for extranodal lesions | |
| size of | ≥15 mm in short axis diameter (SAD) for nodal lesions | |
| measurable | ≥10 mm in LD for clinical lesions (must be measured using electronic calipers) | |
| lesions | ≥20 mm in LD for chest X-ray (if clearly defined and surrounded by aerated lung): CT scan is preferable | |
| | Ultrasound cannot be used to measure lesions | |

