| Lymph nodes | Lymph nodes are considered pathologically enlarged if >10 mm in SAD. To be measurable, nodal lesions must be \geq 15 mm in SAD. Nodal lesions with SAD >10 mm and <15 mm are non-measurable. | |
| | The sum of the diameters (LD for extranodal target lesions, SAD for nodal lesions) is followed through the course of therapy. | |
| Bone lesions | A lytic or mixed lytic-blastic bone lesion with a soft tissue component assessed on CT scan/MRI can be measurable if the minimum size criteria are met. Blastic bone lesions and bone lesions assessed on bone scan, PET, or plain film are non-measurable. | |
| Cystic lesions | Lesions that meet the criteria for radiographically defined simple cysts are not malignant. Cystic lesions thought to be metastases can be measurable if they meet the minimum size criteria. Non-cystic lesions are preferable. | |
| Lesions with prior local therapy | Lesions in previously irradiated areas (or areas treated with local therapy) are not measurable unless the lesion has progressed since therapy. Conditions should be defined in study protocols. | |
| Too small to measure | If a target lesion becomes too small to measure, a default value of 5 mm is assigned. If the lesion disappears, the measurement is recorded as 0 mm. | |
| FDG/PET | New lesions can be assessed using FDG-PET: | |
| | (-) PET at baseline and (+) PET at follow-up is PD based on a new lesion. | |
| | No PET at baseline and (+) PET at follow-up is PD if the new lesion is confirmed on CT. If a subsequent CT confirms the new lesion, the date of PD is the date of the initial PET scan, not the CT scan. | |
| (Eigenhauer et el | No PET at baseline and a (+) PET at follow-up corresponding to a pre-existing lesion on CT that is not progressing: not PD | |

(Eisenhauer et al 2009) LD=longest diameter; SAD=short axis diameter; CT=computed tomography; MRI=magnetic resonance imaging; PET=positron emission tomography; FDG=fluorodeoxyglucose

Evaluation of Target Lesions

Target lesions will be evaluated as follows:

| Response | Criteria | |
|----------|----------------------------------------------------------------------------------------------------------------------------|--|
| CR | Disappearance of all target lesions | |
| PR | At least a 30% decrease in the sum of the longest diameter (LD) of target lesions, taking as reference the baseline sum LD | |

| Response | Criteria | | |

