|----------|-------------------------------------------------------------------------------------------------------------------------------------------------------------------------------------------|--|--|
| PD | At least a 20% increase in the sum of the LD of target lesions, taking as reference the smallest sum LD recorded since the treatment started or the appearance of one or more new lesions | | |
| SD | Neither sufficient shrinkage to qualify for PR nor sufficient increase to qualify for PD, taking as reference the smallest sum LD since the treatment started | | |

Evaluation of Nontarget Lesions

Nontarget lesions will be evaluated as follows:

| Response | Criteria | | |
|------------------------|----------------------------------------------------------------------------------------------------------------------------------------------------------------------------------------------------------------------------------------------------------------------------------------------------------------------------------------------------------|--|--|
| CR | Disappearance of all non-target lesions and normalization of tumor marker level | | |
| Incomplete response/SD | Persistence of 1 or more non-target lesion(s) and/or maintenance of tumor marker level above the normal limits | | |
| PD | Appearance of 1 or more new lesions and/or unequivocal progression of existing non-target lesions. (Although a clear progression of "non-target" lesions only is exceptional, in such circumstances, the opinion of the treating physician should prevail and the progression status should be confirmed later on by the review panel [or study chair].) | | |

Evaluation of Best Overall Response

The best overall response is the best response recorded from the start of the treatment until disease progression/recurrence (taking as reference for PD the smallest measurements recorded since the treatment started). In general, the participant's best response assessment will depend on the achievement of both measurement and confirmation criteria, as follows:

| Target lesions | Non-target lesions | New lesions | Overall response |
|----------------|------------------------|-------------|------------------|
| CR | CR | No | CR |
| CR | Incomplete response/SD | No | PR |
| PR | Non-PD | No | PR |
| SD | Non-PD | No | SD |
| PD | Any | Yes or no | PD |
| Any | PD | Yes or no | PD |
| Any | Any | Yes | PD |

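### Inclusion criterion 7 admits participants with only non-measurable disease, who cannot reach a partial response but are not excluded from the primary ORR, and whose stable disease has no row in the overall-response table

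*Combined protocol and SAP*

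**What the plan says.** **Entry.** Criterion 7 in section 3.1 reads "Presence of at least 1 lesion that is measurable or evaluable using RECIST v1.1". The synopsis has the same alternative: "Presence of at least 1 lesion that is measurable or evaluable using Response Evaluation Criteria in Solid Tumors (RECIST) v1.1". 'Evaluable' is not defined for a lesion.

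**Lesion classes (7.7.1).** Non-measurable disease is a separate class: "Non-measurable lesions: all other lesions including skin lesions, small lesions (less than 10 mm", with ascites and effusions also listed. Target lesions are "all measurable lesions up to a maximum of 5 lesions total and a maximum of 2 lesions per organ".

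**Response rules (7.7.1).** PR requires "At least a 30% decrease in the sum of the longest diameter (LD) of target lesions". Non-target lesions have three categories: CR, incomplete response/SD, and progressive disease (PD). The middle one is "Persistence of 1 or more non-target lesion(s) and/or maintenance of tumor marker level above the normal limits". In the overall-response table, every row ending in CR, PR or SD starts from a target-lesion status. Only the PD rows accept any target status.

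**Who counts for ORR.** Section 7.0 says "Participants must receive a minimum of two 28 day cycles to be considered evaluable for the primary endpoint of ORR", with an exception for early withdrawal through rapid progression. Section 8.4.1 defines a responder by a confirmed CR or PR. Section 8.2.3 makes treated participants with no post-dose response assessment non-responders. Sections 8.2.1 and 8.2.2 define an enrolled set and a safety set; there is no response set.

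**Who is imaged.** Section 7.0 restricts one end-of-treatment scan: "Participants with measurable disease who end treatment on a cycle at which a tumor response assessment is not planned". Section 7.7 likewise ties the 8-weekly response assessments to those who have measurable disease. The on-treatment imaging in 7.2.2.1 and Appendix B has no such limit.

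**The concern.** The trial's main product is an estimate of ORR from about 10 people. If some of them cannot reach PR under the protocol's own rules, the estimate mixes two groups and is no longer the response rate among patients in whom response can be measured. The document does not say whether these participants belong in the denominator. It also does not say how to code one whose non-target disease simply persists, although DCR depends on that code. Both choices would then be made after open-label outcomes are known, in a sample where one participant is worth 10 percentage points.

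**Working it through.** **The plan's own figure.** Section 8.1 states 10 subjects as minimally sufficient, with no target rate, precision, alpha or power for ORR. There is no calculation to reproduce.

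**Tracing a participant with no measurable lesion through 7.7.1**

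1. No measurable lesion means no target lesion and no baseline target sum.
2. PR is a fall in that sum, so PR cannot be assessed. The non-target scale has no PR category.
3. If all non-target lesions disappear and the marker normalizes, the non-target status is CR. The overall table still has no row for it without a target status.
4. If non-target disease persists, the non-target status is incomplete response/SD. No overall row receives it.
5. If disease progresses or a new lesion appears, the PD rows apply.

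As printed, PD is the only overall category this participant can be given. Sections 7.0, 8.4.1 and 8.2 contain no rule that takes the participant out of ORR.

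**Effect on ORR.** Let k of 10 evaluable participants have only non-measurable disease, p be the true response rate in measurable disease, and q the rate at which the others are credited with a CR. The documents give none of these; all values below are assumed.

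Expected ORR = ((10 − k)p + kq)/10, so the shift from p is k(q − p)/10. It is downward only when q < p.

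| p | q | k = 1 | k = 2 | k = 3 |
|---|---|---|---|---|
| 20% | 0 | 18% | 16% | 14% |
| 20% | 5% | 18.5% | 17% | 15.5% |
| 30% | 0 | 27% | 24% | 21% |
| 2% | 5% | 2.3% | 2.6% | 2.9% |

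Example: p = 20%, q = 0, k = 2 gives 8 × 0.20/10 = 16%. The last row shows the shift reversing when q exceeds p.

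**Chance that the case arises.** If a share f of eligible patients has only non-measurable disease, the chance of at least one among 10 is 1 − (1 − f)^10. For f = 5%, 10% and 20% this is 40%, 65% and 89%.

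**Sampling error for comparison.** Exact (Clopper-Pearson) 95% interval for 2/10: 2.5% to 55.6%.

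**Effect on DCR.** Take k = 2, both with persisting disease and no progression, and 4 of the 8 measurable participants controlled. DCR is 6/10 = 60% if the two are read as SD, 4/10 = 40% if not, and 4/8 = 50% if they are left out.

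**The case against.** The strongest reply is that this is a descriptive pilot. No test depends on ORR, the interval is far wider than any plausible dilution, and there may be no such participants. Baseline lesions are documented as target or non-target, so ORR by measurability could be reported from planned data. All of this stands, and it limits the weight of the point.

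Several stronger readings are tempting but not supported:

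- **That the plan expressly counts these participants as non-responders.** It does not. The ORR denominator is never written out, and 8.2.3 covers only treated participants with no post-dose assessment. The wording in 7.7 could even suggest a measurable-disease response population. Inclusion as non-responders is the default reading.
- **That ORR must be biased downward.** This holds only if q < p. Treating absent target lesions as a target CR would even turn persisting non-target disease into an overall PR. That is an artefact of the missing rows, not an intended route to response.
- **That these participants necessarily use up the 10 places.** Section 7.1.7 says at least 10 evaluable, with up to about 20 enrolled. Ten is a floor.
- **That DCR coding is wholly undefined.** The protocol adopts RECIST v1.1, and its table may be an extract. What can be said from the document is that its own table is silent.

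The imaging passages also disagree on chest coverage during treatment (7.2.2.1 against Appendix B) and on the interval after treatment (7.2.3 against 7.2.4 and Appendix B). These passages must be reconciled, but that is a separate matter.

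**Conclusion.** The point holds in a limited form. Criterion 7 admits participants who cannot be a PR under 7.7.1, and no rule keeps them out of the sole primary estimate. On the default reading they dilute ORR by k(p − q)/10 whenever their CR rate is below the response rate in measurable disease: 2, 4 or 6 percentage points for k = 1, 2 or 3 at p = 20% and q = 0. These inputs are assumptions, and k may be 0. Counting everyone also matches the literal definition in 1.3.1, a proportion of all subjects. The loss is therefore one of interpretability, with DCR coding left open, rather than a faulty decision rule. It should still be corrected, because the denominator and the coding can be settled in advance at little cost.

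**What to change.** 1. In 8.2 and 8.4.1, define the primary ORR set as treated, evaluable participants with at least one measurable lesion at baseline. Count the target of at least 10 evaluable on that set, say so in 7.1.7, and list the other participants separately. Alternatively, require a measurable lesion in criterion 7, in both the synopsis and 3.1.
2. Add rows to the overall-response table in 7.7.1 for participants with no target lesion, covering non-target CR, persisting disease and PD. State whether persisting disease counts as SD for DCR.
3. Align the measurable-disease wording in 7.0 and 7.7 with the unrestricted on-treatment imaging in 7.2.2.1 and Appendix B.

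**Cost.** Amendment wording, plus one of the following:

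- A slightly smaller denominator. With 2 responders and k = 2, the estimate is 2/8 = 25% (exact 95% interval 3.2% to 65.1%) in place of 2/10 = 20% (2.5% to 55.6%).
- A few more participants. On average 10/(1 − f) enrolled give 10 with measurable disease: 11.1 at f = 10% and 12.5 at f = 20%, before other losses and within the ceiling of about 20.
- If criterion 7 is changed instead, some candidates with only non-measurable disease could no longer enter.

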3.3 Registration Procedures

Eligible participants will be enrolled on study by the Penn State Cancer Institute, Clinical Trials Office (PSCI-CTO) by the designated Research Study Coordinator. The protocol specific Eligibility Checklist Worksheet must be completed in its entirety prior to enrollment, and source documentation verifying each eligibility criterion must be available. The physician investigator will sign this document acknowledging accuracy of the data including any subjective variables. Following verification of eligibility, it is preferred that participants begin the investigational treatment as soon as possible.

3.4 Early Withdrawal /Discontinuation of the Study Treatment

A participant will be withdrawn from study treatment for any of the following reasons:

- Withdrawal of consent from the study by the participant at any time and for any reason. The reason for elective withdrawal will be documented in the research record if known.
- Unacceptable toxicity in the judgement of the Principal Investigator.
- Toxicity possibly related to abemaciclib does not resolve in14 days.
- Progression of disease requiring alternative systemic treatment.
- Significant participant or protocol noncompliance that, in the opinion of the Principal Investigator, warrants withdrawal of treatment. For example, participant is noncompliant in taking prescribed study medication or fail to return for scheduled follow up visits.
- Development of intercurrent, non-cancer related illnesses or complications that prevent either continuation of therapy or regular follow up.
- In the opinion of the Principal Investigator, it is inappropriate for the participant to continue on the study.
- Best medical interest of the participant at the discretion of the Principal Investigator.
- Subject becomes pregnant.
- Participant become lost to follow up. Participants who are unable to be located despite 3 documented attempts at contact (telephone, mail, or email) followed by a certified letter will be considered lost to follow up and rendered off study.
- Premature study closure.

Every effort should be done to help assure participants who are withdrawn from study treatment undergo the planned end of study follow up, end of treatment follow-up as outlined.3.4.1 Follow-up

An EOT visit will occur 30 ± 7 days from the last study treatment. Follow-up visits will occur every 3 months (\pm /- 7 days) x2, beginning 3 months after last dose of the study drug, then every 6 months (\pm 7 days) thereafter.

